Each subject will be randomized on the day the study is to occur to begin with either NAVA-synchronized or continuous HFNC before crossing over to the other mode to serve as his/her own control. The same RAM cannula will be used in both study arms and will provide a leak of 60-80% as recommended by the product manual. The delivery of high flow during both synchronized and continuous HFNC will be given at two commonly provided levels of high flow: 6 LPM and 8 LPM, given in the same order in each mode (6 LPM then 8 LPM). Each subject will receive 15-minute trials of each mode-level combination, for a total of four trials performed in succession. During each trial, the first 10 minutes will be used for stabilization, and the last 5 minutes will be used for data collection, as has been done in previous trials.^{20, 27-28} There will be approximately one to two minutes between each trial to adjust ventilator settings. Thus, the mode-level combinations of the trials will be as follows: for subjects randomized to begin with synchronized support: synchronized-6 LPM, synchronized-8 LPM, unsynchronized-6 LPM, unsynchronized-8 LPM. For subjects randomized to begin with unsynchronized support: unsynchronized-6 LPM, unsynchronized-8 LPM, synchronized-6 LPM, synchronized-8 LPM.

Title: Effect of Synchronized vs. Continuous High Flow Nasal Cannula using Neurally Adjusted Ventilatory Assist on Work of Breathing in Infants with Bronchopulmonary Dysplasia
 PI: [name]

[figure not shown]

Figure 1. Flowchart depicting order of trials based on initial randomization.

The flows described in the NAVA-synchronized trials refer to the peak flow provided during inspiration. A baseline flow rate of 2 LPM will be provided expiration in these trials (using the PEEP setting corresponding to the appropriate flow rate). During the unsynchronized trials, the continuous high flow rate will be provided (as is common practice with the use of HFNC). During the NAVA-synchronized HFNC trials, the Edi trigger will be set to 0.5 microvolts, apnea time to 5 seconds, back up rate to 10 breaths per minute, and backup pressure settings will be set to provide an estimated peak flow of 6 or 8 LPM according to the designated trial (again, using the pressure setting corresponding to the appropriate flow rate).

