Servo-u ventilators and Servo Tracker Software (Maquet Critical Care, Solna, Sweden) will be used in order to track Edi signal. The MP100 Biopac data acquisition (Biopac Systems Inc., Goleta, CA, USA) will be used to collect data from the monitoring devices. HFNC will be delivered using appropriately sized RAM cannula to allow for air leak around the subject's nares. Persistent (>20 seconds) bradycardia (less than 100 beats per minutes), desaturation (<85%), or hypercarbia (transcutaneous CO₂ >70) will result in cessation of the study.

Title: Effect of Synchronized vs. Continuous High Flow Nasal Cannula using Neurally Adjusted Ventilatory

Assist on Work of Breathing in Infants with Bronchopulmonary Dysplasia

PI: [name]

Risks and Benefits:

Infants often have gagging and may have vomiting when a gastric tube, such as the NAVA catheter, is removed or replaced. Rarely, patients could have a gastric tube go into a place besides the stomach or coil in the esophagus. We should be able to detect if this occurs using the placement screen on the ventilator because the NAVA catheter has electrodes on it that detect the electrical activity of the heart and diaphragm, which can be used to determine the location. In extremely low birth weight infants, transcutaneous monitors (TCOMs) can cause skin burning. These effects are not seen in larger infants like those included in this study. There is a small risk of loss of confidentiality inherent in all research. We will do everything possible to protect the subjects' confidentiality.

There may or may not be direct medical benefit to the subjects involved in this study. The subjects will have continuous carbon dioxide and oxygen monitoring during the study and if any subject has any problems we will be able to detect and respond to this quickly. If a subject shows apparent improvement while using particular HFNC settings, we may be able to suggest to the treatment team that these settings be continued or the current settings adjusted accordingly. If a subject was already performing well on NIV, there may or may not be an improvement during the study. Subjects performing well on NIV will still undergo the trials of settings and interfaces if enrolled in this study. If using synchronized HFNC improves WOB in the subjects included in this study, then we hope the information learned from this study will benefit other infants with BPD needing respiratory support in the future.

Data Handling and Recordkeeping:

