We plan to recruit twenty-four neonates being treated for BPD with NIV. Based on the previous study conducted by Lee et al, using swing Edi to estimate WOB with NIPPV vs NIV NAVA, a 20% reduction in the primary outcome is expected.²⁰ A sample size of twenty-four subjects achieves 81% power to detect a 20% change in the primary outcome. This sample size is based on a two-sided alpha of 0.05. Randomized subjects that do not complete the study will be replaced and will not be included in data analysis. Potential reasons for withdrawal from the study include:

- Serious adverse effects believed to be related to the investigational device
- Intolerable side effects of the study procedures
- Investigator believes it is in the best interest of the subject to discontinue study participation
- Parents request withdrawal from the study

Adverse Event:

An adverse event (AE) is any medical occurrence that develops or worsens in severity during the course of the study, whether or not it has a causal relationship to the study treatment. Concurrent illnesses or injuries should be regarded as AEs. Abnormal results of diagnostic procedures, including abnormal laboratory values, are considered AEs if the abnormality:

Title: Effect of Synchronized vs. Continuous High Flow Nasal Cannula using Neurally Adjusted Ventilatory

Assist on Work of Breathing in Infants with Bronchopulmonary Dysplasia

PI: [name]

- results in study withdrawal
- is associated with a serious adverse event
- is associated with clinical signs or symptoms
- leads to additional treatment or to further diagnostic tests
- is considered by the investigator to be of clinical significance

Serious Adverse Event (SAEs):

An adverse event is “serious” if it involves considerable detriment or harm to one or more persons (who may or may not be subjects), or requires intervention to prevent one or more persons from experiencing considerable detriment or harm. SAEs include

- death
- life-threatening
- requires or prolongs hospital stay
- results in persistent or significant disability or incapacity
- a congenital anomaly or birth defect

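### Excluding and replacing randomized infants who stop early limits the primary swing Edi contrast to infants who tolerate both modes, and may bias it in either direction

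*Combined protocol and SAP*

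**What the plan says.** The rule stands under Sample size and power calculation: "Randomized subjects that do not complete the study will be replaced and will not be included in data analysis". The reasons for withdrawal listed after it include device-related serious effects, intolerable side effects, parental request, and "Investigator believes it is in the best interest of the subject to discontinue study participation".

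Study Design/Procedures places randomization on the day of study. Each infant then has four successive 15-minute trials, both flows of one mode and then both flows of the other, with the flows "given in the same order in each mode (6 LPM then 8 LPM"). Swing Edi is taken from the last 5 minutes of each trial. A heart rate below 100, a saturation below 85% or a transcutaneous CO₂ above 70, lasting more than 20 seconds, "will result in cessation of the study".

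Study Population allows up to 30 infants to be consented so that 24 are retained. Data Analysis plans a paired t-test, or a signed-rank test if assumptions fail, with an unspecified multivariate analysis when necessary. No section names an all-randomized analysis set, a use for partial data, a sensitivity analysis for stops, or a comparison of stops by mode.

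**The concern.** Stops during the trials follow randomization, and the main stopping rule is physiological. Two of its three triggers, saturation and transcutaneous CO₂, are also secondary outcomes. The modes differ in the support they give: continuous flow holds 6 or 8 LPM throughout, while synchronized flow falls to 2 LPM in expiration. Equal tolerance cannot be presumed.

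If infants who do poorly on one mode tend to be those stopped on it, replacing them with infants who tolerate both makes that mode look better than it is. Replacement restores the count of 24 but not the randomized population. The protocol also gives the feasibility of synchronized flow as one of its purposes, and infants who cannot complete it are part of that evidence.

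The all-or-nothing rule also discards usable data when an infant stops in the fourth trial.

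**Working it through.** **1. The plan's own figure.** Inputs from Sample size and power calculation: 24 infants, a two-sided alpha of 0.05, and a 20% change detected with 81% power. No SD is given, so 81% cannot be reproduced from stated inputs. Solving the noncentral t for 81% at n = 24 gives a standardized paired difference of 0.605. The implied SD of within-infant differences is 20/0.605 = 33.1% of the continuous-mode mean. The normal approximation gives (1.960 + 0.878)/√24 = 0.579, or 34.5%. I use 33.1% as an assumption. Other SDs would give other powers: 99.7% at SD 20%, 65.0% at SD 40%, 46.7% at SD 50%.

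**2. Ceiling on losses.** (30 − 24)/30 = 20%. Thirty is the most that may be consented, and randomization comes later, so 20% is an upper bound for losses after randomization.

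**3. Selection model.** Let D = synchronized minus continuous swing Edi. Suppose a fraction p is removed from the top of a latent stop propensity that has correlation ρ with D, so that stops fall on infants doing worse on synchronized flow. With c the upper-p normal quantile and λ = φ(c)/(1 − p):

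- bias = −ρ × SD × λ
- SD among completers = SD × √[1 − ρ²(cλ + λ²)]

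At p = 0.20, c = 0.842, λ = 0.350 and cλ + λ² = 0.417. At p = 0.10, λ = 0.195. With no true effect and 24 completers:

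| Loss | ρ | Bias (points) | Two-sided false-positive rate |
|---|---|---|---|
| 10% | 0.3 | −1.9 | 5.9% |
| 10% | 0.5 | −3.2 | 7.6% |
| 20% | 0 | 0 | 5.0% |
| 20% | 0.3 | −3.5 | 7.9% |
| 20% | 0.5 | −5.8 | 14.0% |

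For example, 0.5 × 33.1 × 0.350 = 5.8. Bias scales with the assumed SD: at 20% loss it runs from 0.3 × 20 × 0.350 = 2.1 points to 0.5 × 50 × 0.350 = 8.75 points over SDs of 20% to 50%. The sign reverses if the stops fall on infants doing worse on continuous flow.

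**4. Four-trial simulation.** Here stopping depends on swing Edi in the mode being run, not directly on D. Assumptions: between-infant SD 40%, baseline stop risk per trial as shown, and log-odds of stopping either unrelated to swing Edi or rising by 1 per SD.

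| Stop risk per trial, synchronized / continuous | Link | True effect | Bias (points) |
|---|---|---|---|
| 8% / 2% | none | – | within 0.1 of zero |
| 8% / 2% | 1 per SD | 0 | −1.5 |
| 8% / 2% | 1 per SD | −20% | −1.0 |
| 2% / 8% | 1 per SD | 0 | +1.4 |
| 2% / 8% | 1 per SD | −20% | +1.8 |
| 5% / 5% | 1 per SD | −20% | +0.4 |

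The bias is smaller than in step 3 because the level of swing Edi in one mode reflects mostly differences between infants and is only weakly tied to D. Losses are not small here: with 2% / 8% and the link, only 76% to 77% complete.

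**5. Lost 6 LPM pairs.** By the trial order, the 6 LPM pair is complete after trial 3 and the 8 LPM pair after trial 4. Only a trial-4 stop leaves a finished pair to discard. With a constant risk of 5% per trial, that share is 0.95³/(1 + 0.95 + 0.95² + 0.95³) = 0.857/3.710 = 23% of stops. Six stops would mean 6 × 0.23 = 1.4 infants. In the 8% / 2% scenario with no true effect, keeping these pairs cut the bias from −1.52 to −1.14 points, about a quarter.

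**The case against.** The stop criteria are heart rate, saturation and transcutaneous CO₂, not Edi, and the documents show no link between them and the within-infant swing Edi difference. Without a link, unequal stops do no harm, as step 4 shows. Some stops need not depend on mode at all: parental request is one. An infant with transcutaneous CO₂ between 70 and 80 may enter under Study Population yet meets the stop value if it persists, whichever mode comes first. The trials are short, losses may be few, and replacement protects power: 81.0% with 24 complete pairs against 72.8% if losses left 20. Stops would also be partly visible already, since adverse events are logged from consent to last device use and an abnormality that leads to withdrawal counts as one.

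Most of this stands as a limit on size and certainty. It does not alter what the rule does to the population analysed.

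A reader might infer more than the documents support:

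- **That the estimate is biased whenever one mode causes more stops.** Unequal stops are not sufficient. Nor are they necessary: equal baseline risks with a link and a true effect gave +0.4 points.
- **That the bias must favour synchronized flow.** It goes the other way if continuous flow causes the stops.
- **That the false-positive rate could be near 57%, with 11.6 points of bias.** That needs 20% loss, all in one mode, and a correlation of 1.0, which is a mathematical limit.
- **That 6 of 30 randomized infants are expected to be lost.** Thirty is a ceiling on consent.
- **That finished 6 LPM pairs are generally discarded.** This happens only with fourth-trial stops.

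**Conclusion.** The concern holds in limited form. Followed as written, the plan restricts the primary contrast to infants who tolerate both modes, and nothing elsewhere corrects this. Bias is possible in either direction, provided stopping is associated with the within-infant swing Edi difference. That is plausible for respiratory stops but not shown.

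The size is unknown because the documents give neither a stop rate nor an SD. It is about 1 to 2 points against a planned 20% effect under the simulation's moderate link, and about 3 to 6 points, with a false-positive rate of about 8% to 14%, at the loss ceiling with a correlation of 0.3 to 0.5. With no link it is essentially zero. These figures rest on the back-solved SD of 33.1% and on assumed stop risks. The loss of 6 LPM pairs is real but small. The change is worth making because it is cheap.

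**What to change.** Define completion as finishing all four trials. Replace the exclusion sentence with wording to this effect: infants who stop early may be replaced so that 24 complete, but every recorded window of every randomized infant stays in the analysis.

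- **Primary model.** Fit all available swing Edi windows with mode, flow, period (first or second mode), sequence and a random infant effect. Report the completers-only paired test alongside.
- **Stops.** Report number and reason by mode, flow and sequence.
- **Sensitivity analysis.** Add one that treats a mode stopped on the physiological criteria as unfavourable for that infant, for example a sign test or worst-rank scoring. It assigns a result even where the other mode was never received, so label it as sensitivity only.

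The cost is slightly more analysis work, with no extra infants or measurements. The fix is partial. Infants stopped in their first mode add little to a within-infant contrast, and a stop often occurs before that trial's 5-minute window is recorded.

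Separately, the transcutaneous CO₂ limits in Study Population (exclusion above 80) and Study Design/Procedures (stop above 70) must be reconciled.

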- **Pulse oximeter probe** (MasimoSET, Irvine, CA, USA) is cleared (K061204). It will be used to measure oxygen saturations and heart rate.
- **MP100 Biopac data acquisition** (Biopac Systems Inc., Goleta, CA, USA) will be used to collect data from the monitoring devices.

Study Population:

Up to thirty subjects at Arkansas Children's Hospital (ACH) will be consented to retain twenty-four participants in the study. Inclusion criteria will include:

- Chronological age greater than 28 days
- Gestational age at birth less than 33 weeks as documented in the subjects' initial history and physical

Title: Effect of Synchronized vs. Continuous High Flow Nasal Cannula using Neurally Adjusted Ventilatory Assist on Work of Breathing in Infants with Bronchopulmonary Dysplasia
PI: [name]

- A diagnosis of BPD, defined for this study as having received supplemental oxygen for greater than or equal to 28 days from birth
- Currently receiving NIV in the form of nCPAP, NIV NAVA, NIPPV, or HFNC

Exclusion criteria will include:

- Post-menstrual age (gestational age plus chronological age) of greater than 50 weeks 0 days
- Oxygen requirement greater than 40% at the time of enrollment
- Transcutaneous CO₂ measurements > 80
- Currently receiving invasive ventilation
- Major congenital anomalies of the heart and/or lungs
- Bilateral phrenic nerve palsy
- Major gastrointestinal malformations, including gastroschisis, omphalocele, and congenital diaphragmatic hernia
- Currently receiving treatment for pneumonia or suspected/confirmed sepsis

Study Design/Procedures:

Parental consent will be obtained prior to study. Synchronized HFNC is not an option on current HFNC devices, which provide only a constant flow of gas. NAVA devices only provide pressure measurements during NAVA in intubated patients, or NAVA using non-invasive nasal prongs (NIV NAVA). Nonetheless, many neonatal intensive care units (NICUs), including the ACH NICU, use nasal cannulas designed for low or high flow, but not approved for nasal CPAP, to attempt provision of nasal CPAP and NIV NAVA. For our study, we will use the cannula currently in use at ACH (RAM cannula, Neotech, Valencia, CA, USA) and as currently FDA approved, and set the NAVA ventilator so that it responds similarly to a HFNC. The RAM cannula will be used to provide both continuous and NAVA-synchronized HFNC.

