The Principal Investigator will carefully monitor study procedures to protect the safety of research subjects, the quality of the data and the integrity of the study. Each subject will be assigned a unique identifying code or number. The key to the code will be kept in a locked file in a research office. Only the principal investigator and sub-investigators will have access to the code and information that identifies the subject in the study. Demographic and clinical information, such as gestational age, date of birth, gender, race/ethnicity, pregnancy complications, and clinical diagnoses, will be obtained from the medical record and kept on a password protected computer. All data will be de-identified after analysis is complete by destroying the code key. De-identified data will be maintained as per UAMS and ACRI policy (currently all data will be kept until the last subject is 21 years of age plus 2 years) and destroyed per institutional guidelines.

Title: Effect of Synchronized vs. Continuous High Flow Nasal Cannula using Neurally Adjusted Ventilatory Assist on Work of Breathing in Infants with Bronchopulmonary Dysplasia
PI: [name]

Data Analysis:

The primary hypothesis is that WOB estimated by swing Edi will be less during synchronized HFNC compared to continuous HFNC. Statistical analysis will be performed in conjunction with the Arkansas Children's Research Institute (ACRI)/University of Arkansas for Medical Sciences (UAMS) Department of Pediatrics Biostatistics program. A randomization list of synchronized vs. continuous HFNC will be provided by the biostatistics team.

Data collected will be checked for outliers and extreme values, as well as distributional assumptions of the parametric statistical tests. Paired sample t-test will be used to compare the primary and secondary outcomes, as well as safety data, under the two NIV methods when such assumptions are met. When necessary, multivariate analysis that may be more powerful in the presence of high correlation between the outcomes will be conducted for both primary and secondary outcomes. When significant deviation from assumptions is encountered, nonparametric alternatives such as Wilcoxon signed-rank test will be used. Statistical analyses will be performed using SAS (Version 9.4, SAS Institute, Cary, NC, USA) statistical software.

Sample size and power calculation:

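### Excluding every randomized non-completer from data analysis takes stopped infants out of the planned safety comparison by mode, and no table of stops by mode is planned

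*Combined protocol and SAP*

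**What the plan says.** Four parts of the combined protocol and SAP bear on this point.

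- **Sample size and power calculation:** "Randomized subjects that do not complete the study will be replaced and will not be included in data analysis". No exception is made for safety. The withdrawal reasons listed next include "Serious adverse effects believed to be related to the investigational device" and intolerable side effects, alongside investigator discretion and parental request.
- **Data Analysis:** a paired t-test (Wilcoxon signed-rank if assumptions fail) is planned for the primary and secondary outcomes "as well as safety data, under the two NIV methods when such assumptions are met". The term safety data is not defined, and no safety set is described.
- **Study Design/Procedures:** heart rate below 100, saturation below 85% or transcutaneous CO₂ above 70, lasting more than 20 seconds, "will result in cessation of the study". Each infant is meant to have four trials in succession: both flows in one mode, then both flows in the other.
- **Adverse event sections:** an abnormal result counts as an adverse event if it "results in study withdrawal". Adverse events are logged from consent to last device use and are reported onward. Under Monitoring, an independent medical monitor evaluates them.

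**The concern.** An infant whose session ends under a stop criterion has not had all four trials and so has not completed the study. That infant is then replaced and left out of data analysis, which is where the comparison of safety data by mode sits. The infants with the clearest evidence of poor tolerance are thus the ones the comparison cannot contain.

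This matters because the Background says synchronized HFNC has not yet been studied in neonates with BPD, and the Innovation section makes its feasibility a question for this trial. The mode that was running when an infant had to be stopped is a direct tolerability result, and the plan provides no place to report it.

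Stops are foreseeable. Entry is refused for "Transcutaneous CO₂ measurements > 80", while the stop threshold is 70, so an infant between 71 and 80 is eligible and would be stopped if the value persisted.

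**Working it through.** **1. The plan's own figures.** The plan gives no stop rate, so there is nothing to reproduce on this point. The one calculated figure in that section is 81% power for 24 infants and a 20% change. It cannot be rebuilt from stated inputs because no SD of the within-infant difference is given. Solving backwards (paired t-test, noncentral t, 23 df) gives a standardized effect of 0.605, so an SD of 20/0.605 = 33.1% of the mean. Nothing below uses it.

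**2. The texts side by side.**

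- A stop criterion ends the session (Study Design/Procedures).
- A randomized infant who does not complete is left out of data analysis (Sample size and power calculation).
- Safety data by mode are compared within data analysis (Data Analysis).
- Hence stopped infants are absent from that comparison, whether safety data means events or measured values.

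The adverse event sections ask for attribution, expectedness and reporting. They do not ask for a tabulation by the mode or flow at onset.

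**3. What a stopped infant could have given a paired test.**

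- Stopped in trial 1 or 2: one mode only. A paired test drops this infant with or without the exclusion sentence.
- Stopped in trial 3: both flows of the first mode, and no completed trial in the second.
- Stopped in trial 4: both modes at 6 LPM, and one mode at 8 LPM. A pair exists, but Data Analysis does not say how the two flows enter the test, so whether it would be used is open.

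The exclusion sentence is therefore only part of the cause. Deleting it would not bring first-mode stops into a paired comparison.

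**4. Chance that the issue arises.** Assume each infant stops independently with probability p. The chance of at least one stop among 24 infants is 1 − (1 − p)^24:

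- p = 2%: 1 − 0.98^24 = 1 − 0.616 = 38%
- p = 5%: 1 − 0.95^24 = 1 − 0.292 = 71%
- p = 10%: 1 − 0.90^24 = 1 − 0.080 = 92%

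**5. What the missing table could show.** With k stops and 24 completers, 24 + k infants start. If all k stops fall in one mode, that is also the number who started that mode. Exact (Clopper-Pearson) 95% intervals:

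| Stops | Rate | 95% CI |
|---|---|---|
| 1 | 1/25 = 4.0% | 0.1 to 20.4% |
| 2 | 2/26 = 7.7% | 0.9 to 25.1% |
| 3 | 3/27 = 11.1% | 2.4 to 29.2% |
| 6 (ceiling) | 6/30 = 20.0% | 7.7 to 38.6% |

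The ceiling comes from Study Population: up to thirty "will be consented to retain twenty-four participants in the study", so 30 − 24 = 6. It is reached only if nobody is lost between consent and randomization, which may be a real gap: "Each subject will be randomized on the day the study is to occur".

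**6. What the table cannot do.** If all k stops fall in one mode, a two-sided exact sign test gives p = 2 × 0.5^k. That is 0.0625 for k = 5 and 0.031 for k = 6. Within the ceiling of six, only a 6 to 0 split falls below 0.05.

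**The case against.** **The events are not lost.** This stands. They are recorded, attributed, reported and evaluated by the medical monitor. A reader might infer that safety information disappears or that oversight fails; the adverse event and Monitoring sections rule that out. They do not, however, plan a comparison by mode.

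**The sentence may mean only the efficacy analysis.** It sits in the sample size section, where the count of 24 is the concern. But it refers to data analysis without limit, and the Data Analysis section names safety data in the same sentence as the primary and secondary outcomes. If the narrow meaning was intended, the fix simply states it.

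**A paired test drops first-mode stops anyway.** This is correct, and it is why the remedy must be an unpaired description.

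**The table would rarely separate the modes.** Also correct, as step 6 shows. Its value is descriptive.

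**Stops among infants who enter with CO₂ of 71 to 80 say little about mode.** This is fair. Such an infant would tend to stop in whichever mode came first, and that is randomized. The overlap makes stops more likely but does not show a mode effect.

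**Conclusion.** The point holds and should be fixed, though its reach is limited. As written, infants stopped on safety grounds contribute nothing to the planned comparison of safety data by mode, and no count of stops by mode is planned. It rests on one inference: that a session ended under the stop rule is a non-completed study. With four successive trials required, that is the natural reading. The size depends on a stop rate that the documents do not give. At 2 to 10%, at least one stop among 24 infants has a chance of 38 to 92%, and the rate among starters can reach at most 20%.

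Two stronger readings are not supported. First, a reader might infer that the trial will report 0/24 stops in each mode and so suggest equal tolerance. The plan produces no stop count, so there would be no such row; the defect is its absence. Second, a reader might infer that the swing Edi result is biased. That would need stops to fall unevenly by mode and to be related to the infant's own difference between modes. The documents show neither, and the change proposed here would not remove such a bias, so it adds nothing to the severity.

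**What to change.** Keep replacement, and keep the completer analysis as primary. Reword the exclusion in the sample size section:

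*Randomized subjects who do not complete all four trials will be replaced and will be excluded from the paired efficacy analysis only.*

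Add to Data Analysis:

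- a safety set of all infants who start at least one trial;
- one descriptive table of stops and adverse events by the mode and flow running at onset, over infants who started that mode, with exact confidence intervals and the reason for each stop, so that parental or discretionary withdrawals appear apart from stop-rule events and device-related or intolerable effects.

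A listing of the recorded data windows from stopped infants, including any 6 LPM pair, is optional. The plan should say that the table is descriptive and has little power at this size.

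The cost is one reworded sentence, one definition and one table. No extra infants, procedures or tests are needed, and the primary analysis and its power are unchanged.
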